2.2.4 Cognitive changes associated with typical aging VS MCI

Cognitive changes observed in typical aging and MCI differ significantly. In this section the changes of each cognitive domain in typical cognitive aging vs MCI will be discussed. Processing speed, a key indicator of cognitive performance, declines with aging (74), and this reduction is more noticeable in People with MCI (PwMCI) (77). Research indicated that in addition to potential deceleration of processing speed in simple tasks, PwMCI might also

encounter significant delays in their reaction times, which are crucial for ensuring safe, appropriate, and efficient interactions within their environments in everyday life (78). Attention declines with normal aging, especially during multitasking (46). However, PwMCI experience more significant attention deficits compared to typical aging (79) in both simple and complex sustained attention and divided attention, suggesting a higher risk of developing dementia (80). The attention deficits in MCI, along with memory and executive function issues, exacerbate difficulties in managing complex tasks such as financial management, learning, and daily routines (81,82). Sensory memory declines with aging (83,84). PwMCI show a significant reduction in sensory memory compared to people with typical cognitive aging (85). These sensory memory issues can make the effortful sensory tasks challenging. For example, listening in noisy environments becomes difficult due to impaired encoding of the stimulus details, making it harder to process and understand speech. This decline affects the ability to retain and integrate fine-grained auditory information, which is crucial for effective communication in complex listening situation (83). PwMCI might also experience difficulties in visual searching tasks (86) which is related to deficits in their sensory memory. Additionally, STM typically declines with age (87). However, this decline is more pronounced in PwMCI who show significant deficits in both visual and visuospatial STM compared to healthy older adults. These impairments can significantly impact the ability to perform everyday tasks that require learning and retention of information (86).

Moreover, in typical aging, WM decline may manifest as slower processing speeds and reduced capacity to hold and manipulate information temporarily, affecting tasks that require multitasking or complex problem-solving. These changes, while noticeable, generally do not severely impact daily functioning (56). However, WM deficits are one of the most common impairments in MCI,

affecting everyday tasks that require sustained mental effort and organization, such as managing finances, following multi-step instructions, and maintaining medication schedules (88,89). In particular, environmental distractors have a disproportionate effect on the WM performance of PwMCI, making it challenging for them to handle tasks that require attentional control and the ability to manage distractions and interruptions. As a result, PwMCI often experience greater susceptibility to memory-related deficits, leading to difficulties in daily functioning and increased vulnerability to developing dementia (88).

In terms of LTM, episodic memory typically declines with aging (90), and this decline is more noticeable in PwMCI than what is expected from typical aging (70). Research shows that PwMCI exhibit significant deficits in tasks requiring the recall of spatial locations and item recognition, reflecting an impairment in episodic memory. These deficits can affect daily activities that rely on recalling recent events or navigating familiar environments (91). In contrast, semantic memory which handles general knowledge learned during life (53) generally remains stable with age (92). However, it declines in PwMCI. This is particularly evident in tasks involving the naming of famous people or recalling factual information, indicating that MCI impacts not only episodic but also person-specific semantic knowledge (91). In contrast to declarative memory, procedural memory and emotional memory remains stable across the lifespan (93) and in MCI (94,95).

Regarding visuospatial skills, basic abilities generally remain intact with normal aging, thought older adults may experience slower processing speeds. In contrast, advanced skills, such as visuospatial memory and mental imagery, typically decline as part of aging process (55). MCI is associated with further impairment in visuospatial skills beyond what is expected from normal aging (55). PwMCI often show deficits in spatial short-term memory, spatial orientation, and the

ability to construct and manipulate spatial representations. These impairments can significantly affect daily activities, such as navigating new environments, remembering the locations of objects, and interpreting complex visual information (55). The decline in visuospatial abilities in MCI can also impact more complex tasks that require the integration of spatial and executive functions, leading to increased difficulty in planning and executing tasks that involve spatial components. For example, individuals with MCI may find it challenging to follow directions, assemble objects, or perform tasks that require an understanding of spatial relationships, which can affect their overall quality of life (55).

Executive functions, including both inhibitory control and cognitive flexibility declines with normal aging (56,74). This decline is more evident in PwMCI, potentially impacting effortful daily routines (96,97). Inhibitory control, the ability to suppress irrelevant stimuli or responses, and cognitive flexibility, the capacity to switch between different tasks or mental states, are essential for effective executive functioning. In people with MCI, deficits in these areas are common and can predict a worse prognosis. These impairments interfere with the ability to organize and process information, resist distractions, and implement strategies for encoding and recall, affecting everyday routines such as managing finances, medication adherence, and other complex tasks. The impairment in executive functions is a marker of potential progression to Alzheimer's disease, making early identification and intervention crucial (97).

Language skills generally remain stable with aging (98). However, specific abilities like naming and verbal fluency might decline with age (99,100). MCI is also linked to subtle language deterioration, signaling a potential progression to dementia (98,100,101). This deterioration includes issues with word retrieval, reduced speech fluency, and changes in syntactic complexity.

Although these language impairments are less severe than those observed in Alzheimer's disease, they are significant enough to impact daily communication (101).

2.2.5 MCI diagnosis

Early detection of MCI is beneficial for several reasons. It facilitates timely access to information and treatments (9). It also allows for the modification of risk factors like smoking, physical inactivity, and social isolation, potentially delaying disease progression (11). Additionally, it assists in identifying potential participants for research, essential for evaluating new treatments (9,12). Early detection enables patients to converse with clinicians and family members about their condition, providing insights into prognosis, care preferences, and future financial planning. (9,10). However, diagnosing MCI is challenging and cannot be confirmed by a single test. People who are concerned about their cognitive abilities should be thoroughly assessed through a detailed history and clinical examination. This evaluation should emphasize cognitive capabilities, everyday functional status, current medications, and any neurological or psychiatric conditions. It is also important to conduct laboratory tests (13). The main aims are to distinguish MCI from typical aging or dementia and to detect any reversible factors contributing to MCI, such as depression, side effects from medications, thyroid issues, or deficiencies in vitamin B12 or folate (13). Cognitive function is assessed using traditional cognitive tests such as the Montreal Cognitive Assessment (MoCA), Mini-Mental State Exam (MMSE), Saint Louis University Mental Status (SLUMS), and Quick mild cognitive impairment (Quickmci). The MMSE is one of the most used cognitive tests measure several cognitive abilities in 5 to 10 minutes. MMSE was shown to have a good test-retest reliability (0.80-0.95) (102-104). MMSE is also concurrently valid (103,104); however, it is not sensitive enough to detect MCI. Sensitivity and specificity have been recorded inconsistently ranging from 13% to 97%, and 60% to 100% respectively, considering this variation in accuracy, MMSE is less reliable for MCI detection, specifically at an early stage (105–108).

The MoCA is one of the most common paper-based cognitive tests that evaluate short-term memory, visuospatial skills, executive function, attention, concentration, working memory, language, and orientation within 10-15 minutes (16). The MoCA demonstrates high test-retest reliability, good internal consistency, as well as strong concurrent and construct validity (109). Content validity is also supported by a high correlation between MoCA and MMSE scores (16). Sensitivity and specificity vary depending on the cut-off points used, with reported sensitivity ranging from 67% to 100% and specificity from 50% to 95% (108). Research also suggested 89% sensitivity and 79% specificity for MCI detection, with the cutoff point of 26 for MCI and 18 for dementia (110). The AUC for MoCA is 0.84 in differentiating MCI from controls. The MoCA is also adjusted for educational level (16). Despite its advantages, the MoCA has some limitations including educational bias for low level of education, associated cost for usage, and the requirement for administrator training (108).

The SLUMS is a cognitive screening tool that can be administered in less than 10 min to assess attention, immediate recall, orientation, delayed recall, calculation, visuospatial abilities, and executive functions (18). However, the SLUMS is less accurate for MCI detection compared to the MoCA, with sensitivity ranging from 73% to 95% and specificity ranging from 65% to 81%, with education adjustment (111). Regarding psychometric properties, although the existing literature offers initial support for the SLUMS, further research is necessary to assess its reliability, validity, and application across more diverse populations (111).

The Qmci is a brief paper-based cognitive test designed to differentiate between normal cognitive function, subjective cognitive disorders, MCI, and early dementia. It assesses

orientation, memory, language, visuospatial skills, and executive function in 3-5 minutes. The Qmci demonstrates good test-retest reliability and validity (112–114). With a cut-off point <62, for MCI detection, it achieves a sensitivity of 90% and specificity of 87%, and the AUC for differentiating MCI form controls is 91% (115). Compared to the MoCA, the Qmci's primary advantage is its brevity, requiring only half the time to complete while offering greater accuracy for MCI detection (115,116). Additionally, the Qmci provides different cut-off points according to both age and educational level (117).

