1.2 Significance of this study

Despite promising applications of SCGs, several research gaps remain. The validities of the applied SCGs are not excellent, and demographic variables, as potential factors associated with cognitive status have been often overlooked. This highlights the need for more comprehensive research to understand how these factors might influence game-based cognitive screenings. Variability in game scenarios and small sample sizes limit the generalizability of findings. Additionally, some tested games lack alignment with older adults' needs and daily tasks or require physical demands that may pose challenges (38). Many applied SCGs were initially developed for healthy users and repurposed for those with cognitive impairments, lacking components simulating daily activities and compelling narratives to motivate maximum performance (39,40). Furthermore, the MMSE has been widely used in numerous studies (39,41), but it is not a precise screening for MCI (42). Investigating the psychological impact, such as state anxiety, of game-based versus traditional screenings has never been examined. In terms of usability, only two previous studies have investigated the usability of game-based screenings for MCI detection, demonstrating good usability for games using touch screens and simulating daily routine (43,44). However, the usability of SCGs using other delivery modes, like computers and mice, has not been explored. Usability is highly dependent on the specific game and its features, necessitating further assessment of different SCGs to confirm their usability for older adults.

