1.3 Research questions

The present study aims to respond the following research questions (RQ).

- 1. Is there any difference between the game performance of older adults with typical cognition and individuals with MCI?
- 2. What is the concurrent validity of the game-based screening for MCI detection?
 - 2.1 Is there any relationship between game performance and total score of traditional cognitive tests (MoCA score and Quick MCI (Qmci)) in older adults with typical cognitive and older adults with MCI?
 - 2.2 Is there any relationship between the sub-MoCA scores and sub-Qmci scores and the game metrics in older adults with typical cognitive and older adults with MCI?

- 3. What is the diagnostic accuracy of the game-based screening assessed by sensitivity, specificity, accuracy, and the Area Under Curve (AUC) of the game-based screening for MCI detection?
- 4. Is game performance an associated factor with cognitive status controlled by demographic variables?
- 5. Is there any difference between the level of state anxiety while playing the G3 game and while administering traditional cognitive tests in older adults with typical cognition and individuals with MCI?
- 6. What is the usability of the G3 as a game-based screening?

2. Literature review

This chapter will address several key areas essential for understanding the use of SCGs in cognitive screening for MCI. It will begin with an overview of cognitive functions and their domains, followed by a discussion of MCI, its prevalence, and associated brain changes. The review will then examine cognitive changes with aging and MCI, traditional cognitive tests used for MCI diagnosis, and their limitations. It will explore digital technologies for MCI screening, focusing on the potential of SCGs. Finally, the chapter will highlight research gaps and propose directions future studies, emphasizing the investigation of the G3, a SCG designed for older adults, for MCI detection.

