3.9 Data analysis

To explore the difference between game performance in PwMCI and healthy comparison group (RQ1), the Unpaired t-test or Mann-Whitney U test as appropriate (155), with an α level of 0.05, will be applied. If the mean difference is statistically significant, it indicates that G3 can classified older adults with typical cognition and older adults with MCI based on their game performance. In addition, a two-way factorial multiple analysis of covariance (MANCOVA) (155) will be performed to compare the effects of demographics as covariates on the differences between groups.

To explore the association between the game performance and traditional cognitive tests, including MoCA and Qmci (RQ2), correlational analysis (155) between the game metrics and the scores of each traditional cognitive tests, including total score sub-scores such as memory and executive functions will be conducted. If the correlation coefficient (r) is positive closer to one, it means that the concurrent validity of G3 as an MCI screening tool is good.

To investigate the diagnostic accuracy of the game-based screening (RQ3), formulas will be used as follows:

Sensitivity: Proportion of true positives correctly identified = $\frac{TP}{TP+FN}$

Specificity: Proportion of true negatives correctly identified = $\frac{TN}{TN+FP}$

Accuracy: Overall correctness of the testx = $\frac{\text{TP+TN}}{\text{Total Population}}$

Where TP: True Positives, TN: True Negatives, FN: False Negatives, FP: False Positives (155). Additionally, the interpretation of the Receiver Operating Characteristic (ROC) and Area Under the Curve (AUC) will be used for examination of diagnostic accuracy (155). The ROC curve is a graphical plot that illustrates the diagnostic ability of a binary classifier system as its discrimination threshold is varied. The curve is created by plotting the True Positive Rate (TPR) against the False Positive Rate (FPR) at various threshold settings (155).

The following steps will be used to calculate the ROC curve:

Firstly, the True Positive Rate (TPR), also known as sensitivity or recall, will be determined using the formula:

$$TPR = \frac{TP}{TP + FN}$$

Secondly, the False Positive Rate (FPR), also known as (1 - specificity), will be determined using the formula:

$$FPR = \frac{FP}{FP+TN}$$

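### The RQ2 rule in 3.9 reads a correlation with MoCA and Qmci scores as validity for MCI screening; it supports association only, and in the expected direction for each metric

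*Protocol*

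**What the plan says.** Section 1.3 frames RQ2 as: "What is the concurrent validity of the game-based screening for MCI detection". Section 3.9 plans correlations between each game metric and the MoCA and Qmci total scores and sub-scores, and fixes the reading in advance: "If the correlation coefficient (r) is positive closer to one, it means that the concurrent validity of G3 as an MCI screening tool is good". No cut-off for r is given.

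Section 3.3 names validity testing, together with diagnostic accuracy, as the primary objectives, and bases the sample size on correlational analysis.

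RQ3 is separate. Section 3.9 plans sensitivity, specificity, accuracy and a ROC curve, with an AUC scale on which 0.5 is no discrimination and the acceptable band starts at 0.7.

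Section 2.2.5 describes the MMSE in two parts: "MMSE is also concurrently valid (103,104); however, it is not sensitive enough to detect MCI". It adds: "Sensitivity and specificity have been recorded inconsistently ranging from 13% to 97%, and 60% to 100% respectively". Section 1.2 says the MMSE is widely used, "but it is not a precise screening for MCI (42". On the MoCA, section 2.2.5 says: "Content validity is also supported by a high correlation between MoCA and MMSE scores (16".

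Section 3.6 lists six game metrics: total playing time, completion, budget management, number of errors, number of list checks, and accuracy from 0 to 100.

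**The concern.** A correlation across the whole sample shows that two scores move together. Whether the game separates people with MCI from people with typical cognition is a different question. The RQ2 rule joins the two by attaching the screening use to the concurrent-validity verdict. Section 2.2.5 does not do this for the MMSE: it grants concurrent validity and then, separately, finds sensitivity for MCI wanting.

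At stake is the wording of a primary result. A good RQ2 verdict phrased in terms of MCI screening could stand beside a weak AUC under RQ3, and the protocol does not say that the screening claim belongs to RQ3 alone.

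There is also a problem of sign. The rule recognises only a positive r, yet for several metrics a better performance is a lower value.

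**Working it through.** **The plan's own figure.** There is none to reproduce, because the RQ2 rule has no cut-off. The values r = 0.60 and 0.70 below are illustrations.

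**Inputs.** MoCA AUC 0.84 for MCI against controls (2.2.5). Two equal groups, 29 and 29 (3.3). Assumed: normal scores, equal SDs within groups, the published AUC holds in this sample, and game scores oriented so that higher is better.

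**Step 1: group gaps in SD units.** Gap = √2 × Φ⁻¹(AUC).
- MoCA, AUC 0.84: m = 1.406.
- Game, AUC 0.60: g = 0.358.
- Game, AUC 0.84: g = 1.406.

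**Step 2: pooled correlation.** For a 1:1 mix with within-group correlation w:

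r = (w + g·m/4) / √[(1 + g²/4)(1 + m²/4)], so w = r × √[(1 + g²/4)(1 + m²/4)] − g·m/4.

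- Game AUC 0.60: the root is √(1.032 × 1.4945) = 1.242 and g·m/4 = 0.126. Then r = 0.60 needs w = 0.745 − 0.126 = 0.62, and r = 0.70 needs w = 0.869 − 0.126 = 0.74.
- Game AUC 0.84: the root is 1.4945 and g·m/4 = 0.4945. Then r = 0.60 needs w = 0.897 − 0.4945 = 0.40, and r = 0.70 needs w = 1.046 − 0.4945 = 0.55.

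All four within-group values are admissible. The same pooled r is therefore compatible with an AUC below 0.7 and with one well above it.

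**Step 3: the limit.** At g = 0 (AUC 0.50) the largest pooled r is 1/√1.4945 = 0.82, reached only when w = 1.

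**Step 4: a natural reference case.** Suppose the game relates to MCI only through MoCA. MoCA's correlation with group is m/√(m² + 4) = 0.575. The game's correlation with group is then 0.575r. Its gap is d = 2(0.575r)/√[1 − (0.575r)²], and its AUC is Φ(d/√2).

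| Pooled r | Game AUC |
|---|---|
| 0.50 | 0.66 |
| 0.60 | 0.70 (0.698) |
| 0.70 | 0.73 |
| 0.90 | 0.80 |

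**Step 5: close to one.** The lowest admissible AUC comes from a game–group correlation of 0.575r − √[(1 − r²)(1 − 0.575²)]. It is 0.59 at r = 0.90, 0.67 at r = 0.95 and 0.76 at r = 0.99.

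**Step 6: sign of r.** MoCA and Qmci rise with better cognition. Accuracy rises with better play, and completion and budget management are coded 1 for success, so a positive r is expected. Playing time and errors fall with better play, so a negative r is expected. Section 2.3.5 reports exactly this for playing time in an earlier virtual-supermarket study (r = −0.2). For list checks the protocol states no direction; negative is expected if more checking reflects poorer memory. For these metrics strong validity would appear as r near minus one, which the rule as written does not recognise.

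**The case against.** The strongest reply is that the rule grades concurrent validity, one psychometric property, and that RQ3 tests detection directly with its own AUC scale. High r with a poor AUC would be reported as good concurrent validity and poor accuracy. Most of this stands, and it is why the point is small. What remains is the phrase tying the RQ2 verdict to screening use, which the correlation does not earn.

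Three stronger readings are tempting, and the documents do not support them.

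- **A reader might infer that RQ2 can endorse a useless screen.** It cannot do so alone, given RQ3. Nor is the MMSE described as useless: section 2.2.5 calls it insufficiently sensitive and less reliable, with reported sensitivity up to 97%. As r approaches one, a worthless game is excluded (step 5).
- **A reader might infer that the MMSE would pass the RQ2 rule.** This is not shown. Its concurrent validity is cited to sources dated 1989 and 1992, before the 2005 MoCA paper, so it cannot refer to agreement with MoCA. The high MoCA–MMSE correlation is offered as content validity of the MoCA, without a coefficient, and no MMSE–Qmci correlation is given. The example shows only that the protocol treats the two properties as distinct.
- **A reader might take the AUC 0.50 and 0.60 cases as likely.** They are bounds. The AUC 0.60 cases require people with MCI to outperform controls at equal MoCA by about 0.51 SD (0.62 × 1.406 − 0.358) or 0.69 SD (0.74 × 1.406 − 0.358, before rounding w), and no reason for that is apparent. Without such a reversal, r = 0.70 gives an AUC of 0.73, already in the acceptable band.

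**Conclusion.** The concern holds as a modest overreach in a stated interpretation rule on a primary objective. A correlation with MoCA or Qmci supports association with those scores. Under normal scores, equal SDs, 1:1 groups and MoCA AUC 0.84, a pooled r of 0.60 to 0.70 does not by itself exclude an AUC below 0.7. If the game relates to MCI only through MoCA, the AUC over that range is about 0.70 to 0.73, at the bottom of the acceptable band. The figures show what r leaves open, not what to expect of G3.

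The requirement of a positive r is wrong for playing time and errors, and probably for list checks. No estimate, test or data item is affected; only the reading of the RQ2 results changes.

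**What to change.** In section 3.9 (RQ2), delete the words that extend the verdict to use as an MCI screening tool, and replace the rule with text to this effect: r in the expected direction for each metric (negative for playing time, errors and list checks; positive for accuracy, completion and budget management) supports concurrent validity with MoCA and Qmci scores; any statement that G3 detects MCI rests on RQ3 (AUC, sensitivity, specificity).

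The cost is two sentences and no new data. The downside is that the RQ2 conclusion becomes slightly less favourable to the game.
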